13.1.6.3 Exploratory Analyses

Analysis of exploratory endpoints will be conducted in the ITT population.

The exploratory efficacy endpoints are the following:

- Change in the MENQOL questionnaire from baseline to Day 57
- Responses to the Usability and Acceptability questionnaire over time

The MENQOL questionnaire consists of 4 domains and is scored as indicated in the Appendix A. Change from baseline for individual domains and total questionnaire score is summarized descriptively by treatment group and time point.

Details of the analysis of the responses to the Usability and Acceptability questionnaire will be outlined in the SAP.

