STATISTICAL METHODS	
General:
 
For the purpose of all safety, efficacy, and other analyses where applicable, baseline is defined as the last measurement before the start of study drug administration.
 
Continuous endpoints will be summarized with number (n), mean, standard deviation, median, minimum, and maximum. In addition, change from baseline values will be calculated at each time point and summarized descriptively. For categorical endpoints, descriptive summaries will include counts and percentages.
 
Analysis Populations:
 
The ITT population, defined as all randomized participants, will be used to summarize participant disposition, demographics and baseline characteristic summaries, efficacy endpoints, and exploratory endpoints.
 
Efficacy evaluations include changes in vaginal pH, changes in vaginal cytology (maturation index; percentage of basal and superficial cells), change in dyspareunia, and change in most bothersome symptom. These will be summarized using the ITT population. For the analysis the exploratory endpoints, results from the MENQOL questionnaire and the Usability and Acceptability questionnaire will be summarized over time from baseline in the ITT population.
 
An analysis of covariance (ANCOVA) model will be used to assess treatment differences in change from baseline for vaginal pH, vaginal cytology, and most bothersome symptom, using baseline score as a covariate. With no formal testing planned for this study, the P values will be informational.
 
The Safety population, defined all participants who are enrolled and receive any amount of planned IP, will summarize the recorded AEs, clinical laboratory safety tests, vital signs, ECG results, physical examination findings, and any other parameter relevant for safety assessment.

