5.4. Summary of Potential Risks and Benefits

The potential benefits of study participation are that participants with VVA may experience a reduction in the symptoms associated with VVA as a result of treatment with DARE-VVA1. No other benefits of participation are anticipated.

The potential risks of study participation include those associated with exposure to tamoxifen and the excipients found in DARE-VVA1 and the risks of medical evaluation, including venipuncture.

Oral tamoxifen (tablets or solution) is approved for the treatment of estrogen receptor-positive metastatic breast cancer and to reduce the risk of breast cancer in women at high risk.¹⁸ The label includes a boxed warning concerning the risk of uterine malignancies, stroke, and pulmonary embolism. General warnings include risks of thromboembolic events (although this risk is greater when co-administered with chemotherapy), embryo-fetal toxicity (which is not a risk in the present study population), and liver cancer and liver abnormalities.

The National Surgical Adjuvant Breast and Bowel Project reported relative risks of serious events in a double-blind, placebo-controlled study of 5 years' treatment with tamoxifen (20 mg per day) designed to evaluate whether treatment would reduce the incidence of invasive breast cancer in high-risk women. After a median treatment duration of 3.5 years in 13,388 women, the rates (per 1,000 women per year) for major outcomes were as follows:

Major Outcomes	Rates for tamoxifen (per 1,000 women per year)	Rates for placebo (per 1,000 women per year)
Endometrial adenocarcinoma	2.20	0.71
Uterine sarcoma	0.17	0.0
Stroke	1.43	1.00
Pulmonary emboli	0.75	0.25
Deep vein thrombosis	1.26	0.79
Cataracts	25.41	22.51

Source: Soltamox label¹⁸

In addition to these serious risks, the most common adverse reactions with oral tamoxifen include hot flashes, mood disturbances, vaginal discharge, vaginal bleeding, nausea, and fluid retention.¹⁸

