6.3. Exploratory Objectives

The exploratory objective is:

- To evaluate the impact of DARE-VVA1 on quality of life using a menopause-specific instrument
- To assess the usability and acceptability of DARE-VVA1

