6.4. Objectives and Endpoints

Objectives	Endpoints
Primary	

 • To evaluate the safety and tolerability of DARE-VVA1 by intravaginal administration 	
 • Adverse events • Clinical laboratory findings • Vital signs results • 12-lead ECG results • Physical examination findings • Change in local site irritation scores from baseline to Day 57 • Endometrial thickness (measured by transvaginal ultrasound) in women who have not undergone hysterectomy prior to the study

 • To determine the plasma PK of DARE-VVA1 after intravaginal application 	
 • Standard PK parameters from noncompartmental analysis on Day 1, with steady-state parameters on Day 56 • Dose-proportionality of tamoxifen

Secondary	

 To evaluate preliminary efficacy and pharmacodynamics of DARE-VVA1 in terms of most bothersome symptom, dyspareunia, and changes in vaginal cytology and pH 	
 Change of vaginal pH from baseline to Day 57 Change in vaginal cytology (maturation index; percentage of basal and superficial cells) from baseline to Day 57 Change in most bothersome symptom from baseline to Day 56 Change in severity of dyspareunia from baseline to Day 56 Correlation between exposure and local changes
Exploratory	

 To evaluate the impact of DARE-VVA1 on quality of life using a menopause-specific instrument To assess the usability and acceptability of DARE-VVA1 	
 Change in the MENQOL questionnaire from baseline to Day 57 Responses to the Usability and Acceptability questionnaire over time

[figure not shown]

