13. STATISTICS

13.1. Statistical Analysis

This section presents a summary of the planned statistical analyses. An SAP that describes the details of the analyses to be conducted will be written prior to database lock.

An analysis of covariance (ANCOVA) model will be used to assess treatment differences in change from baseline for vaginal pH, vaginal cytology, dyspareunia, and most bothersome symptom, using baseline score as a covariate. With no formal testing planned for this study, the *P* values will be informational.

Summary statistics will be provided for the variables described below. For continuous variables, these statistics will typically include the number of participants, mean, standard deviation (SD), median, minimum, and maximum. For categorical variables, these statistics will typically include the number and percentage of participants in each category. The denominator for percentage will be based on the number of participants appropriate for the purpose of analysis.

For all calculations of change from baseline, the last observation recorded before the first administration of the insert (DARE-VVA1 or placebo) will be considered as the baseline observation.

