13.1.6.2 Secondary Analyses

The secondary efficacy endpoints are the following:

- Change of vaginal pH from baseline to Day 57
- Change in vaginal cytology (maturation index; percentage of basal and superficial cells) from baseline to Day 57
- Change in most bothersome symptom from baseline to Day 56
- Change in severity of dyspareunia from baseline to Day 56
- Correlation between exposure and local changes

Descriptive summaries (mean, SD, median, minimum, and maximum) involving change of vaginal pH and vaginal cytology will be presented by treatment group at each time point. In addition, an ANCOVA model will be used to assess treatment differences in change from baseline for vaginal pH, vaginal cytology, dyspareunia, and most bothersome symptom, using baseline score as a covariate. The *P* values will be informational, and no formal testing is planned for this study.

The change in severity from baseline for the most bothersome symptom identified by participants at screening will be summarized categorically by treatment group (see Section 10.3.3.3 for assessment details). In addition, the change in severity from baseline will also be summarized descriptively for each of the 5 symptoms evaluated at each time point.

For assessments of dyspareunia, change in severity from baseline will be summarized descriptively by time point and by treatment group. A categorical summary of severity will be presented by treatment group at each time point.

Pharmacodynamics will be assessed by correlating the dose administered to exposure of tamoxifen in plasma, and then by relating the exposure to local vaginal change in cytology and pH as well as to the reported symptomatology over 56 days. Additional details of this analysis will be provided in the SAP.

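### Section 13.1.6.3 plans no between-arm estimate for MENQOL, the only quality-of-life measure, although a baseline-adjusted ANCOVA is already planned for dyspareunia and most bothersome symptom

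*Combined protocol and SAP*

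**What the plan says.** The exploratory objective (Section 6.3) is "To evaluate the impact of DARE-VVA1 on quality of life using a menopause-specific instrument". Section 6.4 gives it one quality-of-life endpoint: "Change in the MENQOL questionnaire from baseline to Day 57".

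The analysis in Section 13.1.6.3 is: "Change from baseline for individual domains and total questionnaire score is summarized descriptively by treatment group and time point". The synopsis adds only that "results from the MENQOL questionnaire and the Usability and Acceptability questionnaire will be summarized over time from baseline in the ITT population". Neither place names a difference between arms or an interval.

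For the secondary outcomes, Section 13.1.6.2 states that "an ANCOVA model will be used to assess treatment differences in change from baseline for vaginal pH, vaginal cytology, dyspareunia, and most bothersome symptom", with the baseline score as covariate and informational P values. Section 13.1 has the same list. The synopsis list is shorter: "treatment differences in change from baseline for vaginal pH, vaginal cytology, and most bothersome symptom, using baseline score as a covariate". MENQOL appears in none of the three.

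Section 13.1 leaves analysis details to an SAP to be written before database lock. No SAP text is in the document supplied. Within Section 13.1.6.3, only the Usability and Acceptability questionnaire is explicitly deferred to the SAP; the MENQOL method is stated outright.

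**The concern.** The objective asks what the product does to quality of life. In a trial randomised 1:1:1:1:1 with a placebo arm, the contrast with placebo answers that question. MENQOL is self-reported with one-month recall, so some change common to all arms is plausible. A table of mean changes shows this in the placebo column, but the reader must take the difference by eye. With 8 women per arm, part of any apparent difference may come from where the arms happened to start.

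MENQOL suits the planned model at least as well as the symptoms already in it. It has a pre-dose Day 1 score, a Day 57 score and domain means running from 1 to 8 (Appendix A), whereas dyspareunia has four levels. What is at stake is how clearly the quality-of-life result can be read when later studies are designed.

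**Working it through.** **The plan's own figure.** Five groups of 8 (4 hysterectomised plus 4 not) give 5 × 8 = 40, as stated in Section 13.2. No alpha, power, effect size or SD is given, so there is no power figure to reproduce.

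**Patient-reported outcomes, side by side (Sections 13.1, 13.1.6.2 and 13.1.6.3).**

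| Outcome | Tier | Descriptive by arm | ANCOVA |
|---|---|---|---|
| Most bothersome symptom | secondary | yes | yes |
| Dyspareunia | secondary | yes | yes (not in the synopsis list) |
| Dryness, irritation/itching, dysuria, bleeding, each separately | secondary section | yes | no, unless chosen as most bothersome |
| MENQOL domains and overall score | exploratory | yes | no |

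**Assumptions for the arithmetic, none given in the documents.** Scores are in units of the MENQOL SD, equal at both visits. The baseline to Day 57 correlation ρ is 0.5, with range 0.3 to 0.7. There are 8 per arm with no dropout, and intervals are two-sided 95%.

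**Baseline imbalance.** The SD of the difference in baseline means between two arms is √(2/8) = 0.5 SD. An imbalance of that size shifts the raw difference in change by (1 − ρ) × 0.5, which is 0.25 SD at ρ = 0.5 (0.35 at 0.3, 0.15 at 0.7). ANCOVA corrects for this.

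**Half-widths.**
- ANCOVA, one dose against placebo: t(34) × √[(1 − ρ²)(2/8)(1 + 1/32)]. Residual df are 40 − 6 = 34 and t = 2.032. The last factor is an approximate allowance for estimating the baseline slope. At ρ = 0.5: 2.032 × √(0.75 × 0.25 × 1.03125) = 0.89.
- Raw change, variance pooled over five arms: t(35) × √[2(1 − ρ)(2/8)]. At ρ = 0.5: 2.030 × √0.25 = 1.02.
- ANCOVA, 32 active against 8 placebo: replace 2/8 by 1/8 + 1/32. At ρ = 0.5: 2.032 × √(0.75 × 0.15625 × 1.03125) = 0.71.

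| ρ | ANCOVA, one dose v placebo | Raw change, one dose v placebo | ANCOVA, all active v placebo |
|---|---|---|---|
| 0.3 | 0.98 | 1.20 | 0.78 |
| 0.5 | 0.89 | 1.02 | 0.71 |
| 0.7 | 0.74 | 0.79 | 0.58 |

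**Within one hysterectomy stratum.** For 4 against 4, df = 20 − 6 = 14 and t = 2.145. The half-width is 2.145 × √(2/4) = 1.52 residual SD.

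**As a test.** For one dose against placebo, a true difference of 0.8 residual SD would have power of about 0.34, and 1.0 residual SD about 0.49 (noncentral t, df 34). The added model would supply an estimate with an interval, not a usable test.

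**The case against.** The plan follows a recognisable tier: a model for named secondary endpoints and description for the rest. MENQOL is exploratory, no formal testing is planned, and Section 13.2 says the study is not powered. The by-arm table includes placebo and, under Section 13.1, gives n, mean and SD, so a reader can form an unadjusted difference and its interval. The gain in precision over raw change pooled across arms is modest: 1.02 to 0.89 SD at ρ = 0.5, and only 0.79 to 0.74 at ρ = 0.7. The unseen SAP may add a model.

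All of that stands, and it sets the weight low. It does not remove the point. The outcomes already in the ANCOVA are also untested and unpowered, yet they get a between-arm estimate. The by-arm summary cannot supply the baseline adjustment.

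A reader might infer more than the documents support:
- That every other patient-reported change gets an ANCOVA. It does not: four of the five individual symptoms are only described, like MENQOL.
- That the comparison with placebo is never made. The arms are tabulated together, and the SAP has not been seen; the protocol simply specifies no contrast.
- That the plan will declare an effect from change within an arm. No within-arm test or interval is planned for MENQOL.
- That only MENQOL against placebo could reveal vasomotor harm. Section 5.4 does say that "the most common adverse reactions with oral tamoxifen include hot flashes, mood disturbances, vaginal discharge, vaginal bleeding, nausea, and fluid retention", but Section 13.1.4.1 tabulates treatment-emergent events by preferred term and treatment group, where hot flashes would also appear.

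**Conclusion.** The point holds in limited form. The protocol specifies no between-arm estimate or interval for MENQOL, its sole quality-of-life measure, although a suitable baseline-adjusted model is already planned for two other patient-reported outcomes. The main gains from adding it are a stated contrast with placebo and correction of chance baseline imbalance (SD 0.5 score SD between two arms). Tighter intervals are a smaller gain. Even so, a single-dose interval would be roughly ±0.7 to ±1.0 SD wide under the assumed correlations, equal SDs and full follow-up. No stated power is contradicted and no primary or secondary conclusion is affected. This is a worthwhile, optional improvement.

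**What to change.** In Section 13.1.6.3, or in the SAP before database lock, add the four MENQOL domain scores and the overall score to the ANCOVA of Section 13.1: change to Day 57 on treatment, with the Day 1 score as covariate. Report the adjusted difference from placebo with a 95% CI for each dose and for all active doses pooled, labelled exploratory and not adjusted for multiplicity. Keep the descriptive table. State that conclusions on quality of life rest on the contrast with placebo.

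The cost is a sentence or two and one more run of a planned model, with no new data, visits or participants. The downside is 5 scores × 5 contrasts = 25 additional wide intervals. Section 13.1.1 asks for all analyses in both hysterectomy strata as well as overall, which would make 75. Since 4 against 4 gives about ±1.5 residual SD, the text could limit this model to all participants together.

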13.1.7 Interim Analysis

No interim analyses are planned.

13.2. Sample Size Determination

This dose ranging study is not powered for statistical significance. A sample size of 8 participants in each treatment group is considered sufficient to provide information on safety, PK, and PD effects, to guide the design of future studies with DARE-VVA1. A total of 40 participants are planned for this study.

14. STUDY CONDUCT

Steps to ensure the accuracy and reliability of data include the selection of qualified investigators and appropriate study sites, review of protocol procedures with the investigator and associated personnel before the study, periodic monitoring visits, and meticulous data management.

14.1. Sponsor and Investigator Responsibilities

14.1.1 Sponsor Responsibilities

The sponsor is obligated to conduct the study in accordance with strict ethical principles (Section 15). The sponsor reserves the right to withdraw a participant from the study (Section 8.3), to terminate participation of a study site at any time (Section 14.7), and/or to discontinue the study (Section 14.6).

Daré agrees to provide the investigator with sufficient material and support to permit the investigator to conduct the study according to the study protocol.

14.1.2 Investigator Responsibilities

By signing the Investigator's Agreement (Section 17.1), the investigator indicates that he or she has read the protocol carefully, fully understands the requirements, and agrees to conduct the study in accordance with the procedures and requirements described in this protocol.

Investigators should ensure that all persons who are delegated study-related responsibilities are adequately qualified and informed about the protocol, the IP, and their specific duties within the context of the study. Investigators are responsible for providing Daré with documentation of the qualifications, Good Clinical Practice (GCP) training, and research experience for themselves and their staff as required by the sponsor and the relevant governing authorities.

To ensure compliance with the guidelines, the study may be audited by an independent person. The investigator agrees, by written consent to this protocol, to cooperate fully with compliance checks by allowing access to all study documentation by authorized individuals.

14.1.3 Confidentiality and Privacy

Participant confidentiality and privacy is strictly held in trust by the participating investigators, their staff, and the sponsor and their interventions. This confidentiality is extended to cover testing of biological samples and genetic tests in addition to the clinical information relating to participants. Therefore, the study protocol, documentation, data, and all other information generated will be held in strict confidence. No information concerning the study, or the data will be released to any unauthorized third party without prior written approval of the sponsor.

All research activities will be conducted in as private a setting as possible.

The study monitor, other authorized representatives of the sponsor, representatives of the HREC, regulatory agencies, or pharmaceutical company supplying study product may inspect all documents and records required to be maintained by the investigator, including, but not limited to, medical records (office, clinic, or hospital) and pharmacy records for the participants in this study. The clinical study site will permit access to such records.

The study participant's contact information will be securely stored at each clinical site for internal use during the study. At the end of the study, all records will continue to be kept in a secure location

for as long a period as dictated by the reviewing HREC, institutional policies, or sponsor requirements.

Study participant research data, which is for purposes of statistical analysis and scientific reporting, will be transmitted to ICON. This will not include the participant's contact or identifying information. Rather, individual participants and their research data will be identified by a unique study identification number. The study data entry and study management systems used by clinical sites and by ICON will be secured and password protected. At the end of the study, all study databases will be de-identified and archived.

14.2. Site Initiation

Study personnel may not screen or enroll participants into the study until after receiving notification from the sponsor or its designee that the study can be initiated at the study site. The study site will not be authorized for study initiation until:

1. The study site has received the appropriate HREC approval for the protocol and the appropriate ICF.
2. All GCP documents have been submitted to and approved by the sponsor or its designee.
3. The study site has a Clinical Trial Agreement in place.
4. Study site personnel, including the investigator, have participated in a study initiation meeting.

14.3. Screen Failures

Screen failures are defined as participants who consent to participate in the clinical trial but are not subsequently randomly assigned to the IP or entered in the study. A minimal set of screen failure information is required to ensure transparent reporting of screen failure participants to meet the Consolidated Standards of Reporting Trials (CONSORT) publishing requirements and to respond to queries from regulatory authorities. Minimal information includes demography, screen failure details, eligibility criteria, and any SAE.

Participants who fail inclusion and/or exclusion criteria may be rescreened for the study. Participants may only be rescreened once after the original Screening Visit. If a participant is eligible to enter the study after having previously failed screening, the participant will be assigned a new participant identification number.

14.4. Study Documents

14.4.1 Informed Consent

The nature and purpose of the study will be fully explained to each participant (or the participant's legally responsible guardian). The participants must be given ample time and opportunity to inquire about details of the study, to have questions answered to their satisfaction, and to decide whether to participate. Written informed consent must be obtained from each participant (or guardian) prior to any study procedures being performed. A copy of the ICF will be given to the participants for their records.

14.4.2 Good Clinical Practice Documents

The GCP documents are listed below.

- Signed original protocol (i.e., Investigator's Agreement)
- Curricula vitae of all investigators and subinvestigators
- Name and address of the laboratories
- List of laboratory reference ranges, and if available, a quality certificate
- Any other relevant GCP documents

The GCP documents must be received from the investigator and reviewed and approved by Daré or its designee before Daré will authorize shipment of IP to the study site. Copies of the investigator's GCP documents must be retained at the study site in a secure location. Additional documents, including a copy of the protocol and applicable amendment(s), the DARE-VVA1 IB, eCRF completion guidelines, copies of regulatory references, copies of HREC correspondence, and IP accountability records should also be retained as part of the investigator's GCP documents. It is the investigator's responsibility to ensure that copies of all required GCP documents are organized, current, and available for inspection.

A Delegation Log for study-related duties will also be retained at the study site, following signature.

